6.0 Pretreatment Evaluation

A complete history including age, history of use of chronic pain medication, history of anticoagulants and history of allergies to local anesthetics will be obtained within 4 weeks of randomization.

Physical examination including height, weight and body mass index will be recorded within 4 weeks of surgery.

7.0 Evaluation During Study

After surgery, pain can be assessed upon arrival to PACU.

Time to discharge and reason for delay in discharge will be assessed.

A follow-up phone call with the patient will occur three days after surgery to assess pain control as well as patient satisfaction. Participation in the study will terminate after the follow-up phone call three days after surgery.

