2.4 Risks and Side Effects of Caudal Nerve Blocks

Risks and side effects of the caudal nerve block are pain at site of injection, allergic reaction to the local anesthetic, epidural block, subarachnoid block, infection, ineffective block, and injection into blood vessel.

A test dose of the CNB is injected prior to the full dose, to ensure that it is not being injected into the bloodstream. If the full dose of CNB is injected into a blood vessel, which is never done, tachycardia, and subsequently seizure or cardiac arrest may occur.

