- Patients receiving other local anesthetics or agents structurally related to amide-type local anesthetics, toxic effects are additive
- Concomitant administration of CYP1A2 inhibitors
- Debilitated, elderly patients and acutely ill patients
- Heart Block
- Hypotension
- Hypovolemia
- Impaired cardiovascular function
- In brachial plexus block, using 300 mg dose may approach plasma threshold concentrations for central nervous system toxicity
- Injection of small doses in head and neck area may produce adverse reactions similar to systemic toxicity seen with unintentional IV injections of larger doses
- Patients treated with class III antiarrhythmic
- Supraclavicular brachial plexus blocks (higher rate of serious adverse reactions)

Major peripheral nerve blocks (increased risk of intravascular injection and/or overly rapid absorption)

Adverse Effects

COMMON

- Gastrointestinal: Nausea (25%), Vomiting (12%)
- Musculoskeletal: Back pain (5%)

SERIOUS

- Cardiovascular: Bradyarrthymia (9%), Hypotension (37%)
- Neurologic: Parasthesia (6%)
- Ophthalmic: Horner's syndrome pupil (rare)

Drug Interactions

- Bupivacaine (major, probable)
- Ciprofloxacin (moderate, probable)
- Fluvoxamine (moderate, probable)
- Hyaluronidase (major, theoretical)
- St John's Wort (major, probable)

Pregnancy Category

Ropivacaine: B

Breast Feeding

• Ropivacaine: Infant risk cannot be ruled out

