5.3 Postoperative

5.3.1 Pain will be assessed using the numeric rating scale (NRS). The NRS is scored by numeric integers, 0 through 10. The NRS will be used verbally.

- 5.3.2 When using the NRS for pain, the provider will ask, "On a scale of zero to ten, where zero means no pain and ten equals the worst possible pain, what is your current pain level?"
- 5.3.3 Pain will be treated and documented in the PACU dependent on the patient's pain score:
 - Pain score 0-2 receive no treatment
 - Pain score 3-5 receive fentanyl 25mcg iv then reassess pain score in 15 minutes +5min.
 - Pain score 6-8 receive fentanyl 50mcg iv then reassess pain score in 15 minutes +5min.
 - Pain score 9-10 receive fentanyl 75mcg iv then reassess pain score in 15 minutes +5min.
- 5.3.4 If 250 mcg Fentanyl is exceeded, then change to use of Dilaudid 0.5mg IV to a maximum dose of 10mg total.
- 5.3.5 Patients in both groups will be discharged using the same standard PACU discharge criteria. Specifically, patients will be discharged from the PACU when they meet PACU discharge criteria.
- 5.3.6 Pain will be evaluated 15 minutes after arrival to PACU and every 15 minutes thereafter until discharge from PACU. If the patient has been discharged on the day of surgery, the follow-up will be performed by telephone call directly to the patient. Time to discharge, frequency of pain medications and pain medication totals will be recorded.

- 5.3.7 Pain will be evaluated using the NRS with scores of 0-10, where 0 is no pain and 10 is the worst pain. Pain will also be evaluated by the amount of IV and oral pain medicine administered in the first 24 hours post-operatively.
- 5.3.8 Equianalgesic values of IV morphine in mg will be tallied based on each patient's total pain medication administration.
- 5.3.9 An additional follow-up telephone call will occur 3 days after surgery to evaluate pain and amount of pain medications taken.

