- 5.3.10 After surgery, pain will be evaluated subjectively by asking patients their pain score using the NRS of 0-10 immediately after surgery. If unable to assess due to heavy sedation, mark unable to assess and reassess every 15 minutes thereafter. The morning after surgery the amount of intravenous and oral pain medication received by the patient will be assessed. If the patient has been discharged this will occur by follow-up telephone conversation. Adjustment of the patient's oral pain regimen may be necessary if the patient is not receiving relief upon follow up evaluation. This will be assessed on an individual basis.

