8.0 Evaluation of Toxicity

Any side effects from the CNB will be noted including but not limited to side effects from block placement such as subarachnoid puncture, spinal anesthesia, epidural spread, hypotension, and hematoma. We will also assess toxicity from the local anesthetic agents with epinephrine including pre-seizure excitation, seizures, cardiac arrest, epinephrine absorption and desaturation from sedation.

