10.0 Criteria for Removal from the Study

Any patient requesting withdrawal from the study will be removed. Otherwise, study participation will terminate after the three day follow-up telephone conversation has been completed.

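### Neither scheduled contact after PACU includes a stated side-effect question, and section 8.0 covers only block-related events with no timing or method, so delayed events may be under-counted and not collected alike in both arms

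*Combined protocol and SAP*

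**What the plan says.** All references are to the combined protocol and SAP.

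- **Next-morning contact (5.3.10):** "The morning after surgery the amount of intravenous and oral pain medication received by the patient will be assessed". It is made by telephone if the patient has gone home.
- **Day-3 call (5.3.9):** "An additional follow-up telephone call will occur 3 days after surgery to evaluate pain and amount of pain medications taken".
- **Day-3 call (7.0):** "A follow-up phone call with the patient will occur three days after surgery to assess pain control as well as patient satisfaction".
- **End of participation (7.0):** "Participation in the study will terminate after the follow-up phone call three days after surgery". Section 10.0 repeats it: "study participation will terminate after the three day follow-up telephone conversation has been completed". Neither section mentions an event that is unresolved at that time.
- **Toxicity (8.0):** "Any side effects from the CNB will be noted including but not limited to side effects from block placement such as subarachnoid puncture". The list goes on to include hematoma. The section names no contact, question or time window.
- **Named risks:** section 2.4 lists injection-site pain and allergic reaction, then "epidural block, subarachnoid block, infection, ineffective block, and injection into blood vessel". Section 3.0 gives paresthesia at 6% and back pain at 5% for ropivacaine.
- **Analysis (11.3):** adverse events are summarised as counts and percentages, and Fisher's exact or chi-square tests are planned for categorical variables.
- **Reporting:** section 12.0 refers to Appendix A for adverse-event reporting. Section 13.0 makes the principal investigator responsible for submitting adverse events to the IRB.

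**The concern.** Some of the risks that the protocol names can appear or persist after the patient leaves PACU: infection, hematoma, altered sensation, back or injection-site pain. By then the only scheduled study contacts are the two described above, and their stated contents are about analgesia and satisfaction. Whether a delayed event reaches the database then depends on the patient raising it or on someone noticing it in hospital.

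Two features of the plan make that a weak method.

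1. Section 11.2 says patients are blinded. A patient who does not know whether he had a block has little reason to mention numbness during a call about pain and satisfaction.
2. Section 8.0 concerns side effects of the block. An event must first be attributed to the block before the section applies, and no equivalent collection in the GA-only arm is described. Adverse-event percentages set side by side under 11.3 could then reflect how events were sought as well as how often they occurred.

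At stake is how the safety result can be read. Section 2.2 states that nothing has been published on caudal block for this operation, so the trial's complication count is likely to be cited. A low count is reassuring only if events were looked for.

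**Working it through.** **1. Stated content of each contact after PACU, set against the named risks**

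| Contact | Stated content | Side-effect question stated? |
|---|---|---|
| Next morning (5.3.10) | Amount of IV and oral analgesic; oral regimen may be adjusted | No |
| Day 3 (5.3.9) | Pain; amount of analgesic | No |
| Day 3 (7.0) | Pain control; satisfaction | No |

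Hematoma is named in 8.0. Infection (2.4) and paresthesia (3.0) are named as risks but not in the 8.0 list, although the open wording of 8.0 would admit them. Back or injection-site pain could surface under the day-3 pain question. Numbness, fever or swelling has no stated prompt.

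**2. The plan's own figure**

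The only design figure nearby is the power in 11.2: at least 81% with 52 per arm, means 21.6 and 13.9 (difference 7.7), SD 13.6, two-sided 0.05. A fixed-sample normal calculation gives 82.3% and the noncentral t gives 81.6%. Simulating the two-look design with the stated boundaries gives 82.2% without the futility rule and 81.2% with it. The figure reproduces. It does not depend on adverse-event collection.

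**3. Illustration of scale**

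Inputs: 52 block patients (11.2); 6% and 5% (3.0). The two rates are general ropivacaine figures from a monograph covering many uses. Applying them to a caudal block is an assumption.

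- Expected paresthesia: 52 × 0.06 = 3.1.
- Expected back pain: 52 × 0.05 = 2.6.
- Chance of at least one paresthesia: 1 − 0.94^52 = 96%.

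Let c be the share of cases that reach the record. The documents do not give it, so a range is shown. Expected recorded cases are 3.12 × c, and the chance of recording none is (1 − 0.06c)^52.

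| c (assumed) | Expected recorded | Chance of recording none |
|---|---|---|
| 100% | 3.1 | 4% |
| 75% | 2.3 | 9% |
| 50% | 1.6 | 21% |
| 25% | 0.8 | 46% |
| 0% | 0 | 100% |

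**4. What a clean record would show**

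If no event of a given kind is recorded in 52, the one-sided 95% upper limit for its rate is 1 − 0.05^(1/52) = 5.6%. That holds only with full capture. With capture share c the limit becomes 5.6%/c: 11.2% at c = 50% and 22.4% at c = 25%.

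The documents give no rate for infection or hematoma, so no expected count can be given for them. None of these figures estimates how many events this trial would miss.

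**The case against.** The strongest reply is that 8.0 already commits the trial to noting any block side effect. It is open-ended, has no time limit, is not confined to PACU, and names hematoma. Section 7.0 also records the reason for any delay in discharge, which would reveal a complication that prolongs the stay. Section 2.1 says nearly all of the 2013 patients stayed overnight, so many patients may still be in hospital the next morning. The descriptions of the contacts state their purpose and need not be complete question lists. Appendix A may set the collection window and the follow-up of open events. Safety is not a listed objective.

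Most of this stands, and it rules out a stronger reading. A reader might infer that delayed infection, hematoma or paresthesia would go uncounted, that nobody ever asks about side effects, or that open events are abandoned on day 3. The documents do not support those statements. Events volunteered, or seen in hospital, can be recorded under 8.0, and an appendix that is not in the available text cannot be treated as silent.

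The reply does not remove the narrower point. A promise to note events is not a method of finding them, and 8.0 gives none. A patient discharged the next morning has only the day-3 call left. The limitation to block side effects leaves the control arm without a described counterpart, while 11.3 summarises adverse events. Sections 7.0 and 10.0, as written, end participation without qualification or a cross-reference to Appendix A.

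**Conclusion.** The concern holds in limited form. No side-effect question is stated for either contact after PACU, and 8.0 sets no time, method or window and is worded for the block only. Delayed events may therefore be under-counted, and the main text does not provide for collecting them alike in both arms.

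The size of any under-count cannot be derived from the documents. The figure of about 3 paresthesia cases in 52 is illustrative, because the rate is not specific to caudal block and nothing says that such cases arise or persist after PACU.

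The point about collection rests on the stated contact contents being what staff will follow. The point about events open at day 3 is conditional: it holds only so far as Appendix A does not already provide for them. Power, sample size and the primary analysis are unaffected. This is an inexpensive improvement to the safety data and does not call the design into question.

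**What to change.** - **5.3.9, 5.3.10 and 7.0:** add a short fixed side-effect question list to the two existing contacts, with the same wording in both arms. It could cover new numbness or weakness, back or injection-site pain, fever or local swelling, nausea or vomiting, and unplanned care.
- **8.0:** refer to that list, apply it to both arms whether or not an event is attributed to the block, and state the collection window, consistent with Appendix A.
- **7.0 and 10.0:** state that an adverse event still open at the day-3 call is followed as Appendix A provides or, if Appendix A is silent, until it resolves or stabilises. If Appendix A already covers this, a cross-reference is enough.

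No new visit is needed. The documents schedule no postoperative surgical visit, so the change should not rely on one.

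The cost is one amendment, a few more minutes per call, and later closure for the few patients with an open event.

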8.0 Evaluation of Toxicity

Any side effects from the CNB will be noted including but not limited to side effects from block placement such as subarachnoid puncture, spinal anesthesia, epidural spread, hypotension, and hematoma. We will also assess toxicity from the local anesthetic agents with epinephrine including pre-seizure excitation, seizures, cardiac arrest, epinephrine absorption and desaturation from sedation.

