2.0 Background

2.1 Penile Prosthesis Surgery and Anesthesia

According to the Prostate Cancer Foundation, prostate cancer is the most common non-skin cancer in America, affecting 1 in 6 men. In 2014 approximately 233,000 men will be diagnosed with prostate cancer (1). Regardless of whether the nerves were spared during surgery or whether the most precise dose planning was used during radiation therapy, nearly all men will experience some erectile dysfunction for the first few months after treatment (2). The majority of these men will not require penile prosthesis surgery, however, a significant subset will. In addition, there are other factors that may lead to the decision for penile prosthesis surgery such as severe diabetes, pelvic trauma or neurological dysfunction. Each year, about 20,000 American men opt for a penis implant, according to the Cleveland Clinic (3).

In 2013, fifty-eight penile prosthesis surgeries were performed here at MD Anderson. Traditionally, this surgery is performed under general anesthesia. Nearly all of these patients experienced an overnight stay in the hospital as well as a hospital course that included difficult pain control with conventional narcotics and anti-inflammatory drugs.

Alternative forms of anesthesia for patients undergoing penile prosthesis surgery have been sought to reduce postoperative pain and eliminate the need for an overnight stay. In an era where medical costs and patient preference have led to an increase in the number of outpatient surgical procedures, regional anesthesia is being increasingly utilized. Proposed advantages of regional anesthesia include decreased neuroendocrine "stress" response and improved postoperative pain control. It also reduces medical costs by decreasing the need for postoperative opioid analgesics, antiemetics and hospitalizations (4). Regional anesthesia in the form of a caudal nerve block (CNB) has been utilized as an alternative or adjunct to general anesthesia. A CNB can provide patients with anesthesia during the procedure in addition to the possible effect of decreased postoperative pain, nausea, vomiting and decrease their length of hospitalization.

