5.0 Treatment Plan

5.1 Preoperative

- 5.1.1 After consents for surgery and study participation are signed, patients will be registered for the trial by the research staff. Patients will be randomized (1:1) using a computerized randomization scheme.
- 5.1.2 Patients will be randomized (1:1) to one of two groups:
 - Group I, Treatment Group: Patients receive a caudal nerve block prior to surgery and receive general anesthesia during surgery.
 - Group II, Control Group: Patients receive general anesthesia during surgery without a caudal nerve block.
- 5.1.3 Patients in both groups will receive Famotidine 20mg IV, up to 1-2mg IV Midazolam and 25-50mcg IV Fentanyl in the holding area prior to the start of surgery.
- 5.1.4 Patients who are age 70 and older will not receive Midazolam 2mg IV in the holding area prior to the start of surgery.
- 5.1.5 Patients in Group II will receive Fentanyl 50-250mcg IV in the holding area prior to the start of surgery.

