11.3 Analysis Plans

Patients' demographic information at baseline will be collected. We will use mean, standard deviation, median, and range to summarize continuous variables such as blood pressure, heart rate, temperature, pain medication usage, pain and nausea scores, and frequency counts and percentages for categorical variables such as adverse events. We will use the student t-test or the Wilcoxon rank sum test to compare continuous variables between two patient groups. The Fisher's exact test or Chi-square test will be applied to assess the association between two categorical variables. Linear regression will be utilized to assess the effects of patient prognostic factors on the post-operative pain medication usage and the pain score in the first 24 hours.

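### Section 8.0 defines toxicity by attribution to the block, so unless Appendix A requires equal capture, any between-arm comparison of adverse events would be biased against the block; the nausea score in 11.3 has no stated collection step.

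*Combined protocol and SAP*

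**What the plan says.** Section 8.0 sets out the toxicity evaluation in two sentences. The first reads "Any side effects from the CNB will be noted including but not limited to side effects from block placement" and gives examples that include hypotension. The second reads "We will also assess toxicity from the local anesthetic agents with epinephrine including pre-seizure excitation, seizures, cardiac arrest, epinephrine absorption and desaturation from sedation". Both are tied to the block or to the drug injected with it.

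Section 5.1.2 describes Group II: "Patients receive general anesthesia during surgery without a caudal nerve block". Section 5.2.3 also rules out local anesthetic field blocks in both groups.

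Section 11.3 plans "frequency counts and percentages for categorical variables such as adverse events" and, among the continuous variables, lists "pain medication usage, pain and nausea scores". It then gives a general sentence on Fisher's exact or Chi-square tests for pairs of categorical variables.

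Section 2.1 names nausea among the hoped-for benefits of the block: "possible effect of decreased postoperative pain, nausea, vomiting and decrease their length of hospitalization".

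Section 12.0 refers adverse-event reporting to Appendix A, which is not in the reviewed text. Section 13.0 makes the principal investigator responsible for submitting adverse events to the IRB.

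**The concern.** A toxicity definition that depends on presumed cause can only be met in the arm exposed to that cause. Staff who follow 8.0 literally would note a fall in blood pressure in Group I as a possible block effect, and would have no instruction in that section to note the same fall in Group II. The anesthesiologist who performs the block knows the assignment, and section 11.2 names only the patients as blinded, so attribution would be made by people who know the arm.

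At stake is the safety summary. Unequal ascertainment makes the block look worse than it is, and no analysis can repair this afterwards. Opioid-related effects, such as nausea and sedation, are where an opioid-sparing technique might be expected to help. These are also the events that 8.0 gives least reason to look for in the control arm.

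The nausea score is a smaller and separate matter: 11.3 intends to summarise a variable for which the text gives no scale, time point or assessor.

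**Working it through.** **1. The plan's own figure.** The only stated power is for the primary endpoint (11.2), at least 81% with 52 per arm. The difference is 21.6 − 13.9 = 7.7 mg and the SD is 13.6. The standard error is 13.6 × √(2/52) = 2.667, and 7.7/2.667 = 2.887. Power is about Φ(2.887 − 1.960) = 82.3%. Simulating the two-stage design with the stated bounds gives 81.3%. The figure reproduces, and the present point does not depend on it.

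**2. Which events on the 8.0 list can arise in which arm.**

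| Item | Group I | Group II |
|---|---|---|
| Subarachnoid puncture, spinal anesthesia, epidural spread, hematoma from block placement | yes | no, there is no block |
| Local anesthetic toxicity, epinephrine absorption | yes | no, these drugs are not given by block |
| Hypotension | yes | yes, under general anesthesia |
| Desaturation from sedation | yes | yes; 5.1.3 provides sedative and opioid premedication in both groups |

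The first two rows are properly confined to Group I. The last two are shared events placed under a block-specific definition. No other section of the reviewed text asks for them in both arms as events.

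**3. Where nausea is collected.** Sections 5.3 and 7.0 cover the pain NRS, analgesic use, time to discharge, reason for delay and satisfaction. Section 6.0 covers history and physical examination. None mentions nausea.

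**4. Size, as an illustration only.** The inputs are the general ropivacaine rates in section 3.0 (hypotension 37%, nausea 25%, vomiting 12%, bradyarrhythmia 9%) and 52 per arm from 11.2. These are drug-information figures, not estimates for this procedure or trial.

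Expected block-arm counts are 0.37 × 52 = 19.2 for hypotension and 0.25 × 52 = 13 for nausea. Fisher's exact test, two-sided, with 19/52 in the block arm:

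| Control count recorded | p |
|---|---|
| 0/52 | 5.1e-7 |
| 10/52 | 0.079 |
| 19/52 | 1.0 |

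If the true count were 19 in each arm, these rows would correspond to none, about half and all of the control events being recorded. The control counts are assumptions.

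**5. How easily a false signal appears.** Assume the same true rate in both arms and no control events recorded. Five against zero gives p = 0.057 and six against zero gives p = 0.027, so the chance of p ≤ 0.05 is the chance of six or more events among 52:

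| Common true rate | Control unrecorded | Both recorded |
|---|---|---|
| 5% | 4% | 1% |
| 9% | 33% | 2% |
| 12% | 60% | 2% |
| 25% | over 99% | 3% |
| 37% | over 99% | 3% |

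The middle column is an upper limit, because it assumes complete non-recording in Group II.

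**The case against.** A reader might infer that side effects are recorded only in the block arm and that the comparison is one-sided by construction. The documents do not support that. Appendix A may contain general adverse-event rules; its absence from the reviewed text is not a fault of the plan. Section 13.0 has adverse events submitted to the IRB without limiting them to the block, and 11.3 likewise names adverse events without restriction. Section 11.3 also summarises blood pressure and heart rate and compares continuous variables between groups, so some hemodynamic data are expected from both arms. Desaturation from sedation could be noted in either arm. All of this stands, and it makes 0/52 a worst case.

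A reader might also infer that the plan commits to a between-arm test of adverse events. It does not say so: it ties only counts and percentages to adverse events, and the Fisher or Chi-square sentence is generic.

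Finally, a reader might conclude that nausea is never collected and that a benefit on nausea or sedation could not be shown. This argues from silence. Blood pressure, heart rate and temperature also appear in 11.3 without a collection step in sections 5 to 7, so those sections are evidently not a complete data list. Section 5.3.10 has staff mark patients too sedated to assess, without restriction by arm. Nausea is not an objective, endpoint or response criterion.

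What survives is narrower. IRB submission is not the same as systematic, equal ascertainment for analysis, and continuous blood pressure data do not define a hypotension event. Section 8.0 remains the only stated definition of what is evaluated, and it is worded by attribution.

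**Conclusion.** The point holds in conditional form. As worded, 8.0 asks for events attributed to the block and its local anesthetic, and nothing else in the reviewed text asks for the shared events in Group II. Unless Appendix A already requires equal capture, any comparison of adverse events between arms would be biased against the block.

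The size of that bias cannot be determined from the documents. The hypotension illustration runs from no distortion (19/52 in both arms, p = 1.0) to the worst case (19/52 against 0/52, p = 5.1e-7). It rests on general ropivacaine rates and on assumed control counts. No figure in the plan is shown to be wrong, and the primary endpoint, N = 104 and its power are untouched.

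The nausea item is a gap in specification: collection is not described. It should not be read as proof that nausea will go unmeasured.

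**What to change.** Reword 8.0 so that one list of events (hypotension, bradycardia, desaturation or sedation, nausea, vomiting) is recorded in both arms, over the same period and by the same method, regardless of presumed cause. Report block-placement complications separately, for Group I only. If Appendix A already requires equal capture, a cross-reference in 8.0 is enough.

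For the nausea score in 11.3, do one of two things: state the scale and when it is taken in both arms, using assessments that already exist (the 15-minute PACU checks and the day-3 call), or delete it from 11.3.

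The cost is a wording change and slightly more data entry in the control arm. If nausea is scored, there is also one item repeated at the chosen contacts. No extra visits are needed, and sample size and power are unaffected.
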